Protocol Title **A study to assess change in weight over six months in Prader-Willi Syndrome**

Date **February 22, 2018**

Principal Investigator [name].
Director of Research Programs
Foundation for Prader-Willi Research
[contact]
[contact]

Co-Investigators [name].
Associate Director of Translational Research Programs
Foundation for Prader-Willi Research
[contact]
[contact]

[name].
Associate Director of Research Programs
Foundation for Prader-Willi Research
[contact]
[contact]

Sponsor Name Foundation for Prader-Willi Research (FPWR)
[name]
[name]

Sponsor Study Number 2018_01

Confidentiality Statement: Information contained within this document is not to be disclosed in any way without the prior permission of the Principal Investigator.

I. Objectives

The primary objectives of the study are:

1. Perform a real-world study of weight changes over 6 months in PWS children and adults aged 12 and over.
2. Study factors that could directly or indirectly affect weight change such as diet, medication, food access and environment.
3. Collect data on participant height change over 6 months to calculate body mass index (BMI)

II. Background and Introduction

Prader-Willi syndrome (PWS) is a complex neurodevelopmental disorder resulting from disruption of an imprinted region of chromosome 15 (15q11.2-q13). PWS has an estimated incidence of 1:15,000-1:30,000 births worldwide, and equally affects males and females of all ethnicities. PWS

is characteristically associated with feeding difficulties and failure to thrive in infancy and early childhood, followed by the development of excessive eating (hyperphagia), intense food seeking behavior, and morbid obesity. Additional features of PWS include poor muscle tone and strength (hypotonia), hypogonadism, osteoporosis, scoliosis, infertility, delayed motor and language development, impaired cognition, sleep abnormalities, behavioral challenges including tantrums, obsessive compulsiveness and skin picking, and psychiatric illness in adulthood. The phenotype exhibits a broad spectrum of severity.

The incidence and natural history of several PWS symptoms are poorly defined. Gathering data on these is essential not only to understand the development and severity of each symptom without relying on anecdotal evidence, but also to appropriately direct therapeutic efforts and clinical trials.

For this study, we will gather and analyze data on changes in body weight over a 6-month interval, roughly the time frame for a clinical trial, for individuals aged 12 and over to focus on age groups that are likely to be recruited in hyperphagia trials. It has previously been shown that weight changes in PWS may depend on age- and nutritional stages (Miller et al 2011), however, larger datasets across different age groups, with frequent measurements, are required to fully understand real world data regarding weight gain and obesity in PWS.

Weight may also be influenced by living situation, diet, medication and access to food. Therefore, we will also survey participants on diet and medication changes and food access, and study the extent to which these may play a role in any observed weight change.

Participants will be recruited from the U.S. and Canada through patient advocacy websites, Facebook and email. Interested participants will sign an informed consent prior to enrolling in the study.

III. Study Design

- We will utilize a commercially available text messaging based clinical app called Mosio (HIPAA and CFR Part 11 compliant) to collect data. (www.mosio.com)
- We will recruit up to n=300 participants. We expect to be able to recruit this number over 1-2 months prior to data collection (6 months).
- The study is expected to last 9 months, with 2 months for recruitment and start up, and 7 months for data collection.
- Mosio will create "Storylines"- a series of questions/surveys, that will be sent at pre-scheduled intervals, as and when participants sign-up.

Data to be collected:

1. Initial Survey at baseline only

- Was PWS diagnosis made by blood test.
- Gender
- Age
- Does the person receive growth hormone (GH) therapy? If yes, what age was therapy initiated? If no, were they ever on GH therapy? Age at initiation and how long were they on it.

- In the past 6 months, approximately how often did you weigh your child with PWS?
daily, weekly, monthly, less than monthly, only at doctor visits.
2. **Weight**- Once a week, every week, for 6 months. Participants will be sent a pre-scheduled text message reminder to weigh in and send a text response with the participant's weight.
 3. **Survey**-At 3 months and 6 months participants will answer a survey-
 1. Has there been any change in the living situation for the person with PWS in the last 3 months (example: moved, change in primary caregiver, illness in the family etc.? Y/N
 2. To your knowledge has access to food at home or outside the home increased/decreased/stayed the same for the person with PWS?
 3. Has the activity level in the last 3 months increased/decreased/stayed the same for the person with PWS?
 4. Has there been medication change in the last 3 months for the person with PWS? Y/N
If yes-
Please list drug- and select start/stop/increased dose/decreased dose. Will provide option to list more than one drug.
 5. Please record participant's height.

Data will be stored in a secure database. Researcher will be given a log-in and have access to patient data throughout the course of the study.

IV. Duration of study

Study is expected to last 9 months with 3 months for recruitment followed by 6 months of data collection.

V. Eligibility and Recruitment of Participants

a. Inclusion Criteria

Male and female individuals diagnosed with PWS, 12 years and older.

b. Exclusion Criteria

- younger than 12
- non-PWS

c. Sample Size

Target sample size is 300 participants for this study

d. Recruitment of Participants

Participants will be informed of the study via website and social media outlets. These include patient advocacy websites, email, and the Global PWS Registry.

VI. Process of Obtaining Consent

Submission of information by participant or their representative: Participants will be provided details about the study, which will be posted on patient advocacy websites, Facebook, email and other social media outlets. They will be provided contact information and given every opportunity to read, understand and ask questions about the study via electronic means or phone. A consent form will be created on SurveyMonkey and a link to the consent form will be included with recruitment materials.

If they wish to participate in the study, participants or their parent/representative will be directed to an electronic informed consent form where they will be asked to review and sign an informed consent. Individuals providing consent will be asked to confirm that s/he is the participant or legally authorized representative of the participant. Consent from a legally authorized representative is required for participants who are minors or who are over the age of 18 but unable to provide informed consent. Because individuals with PWS have some degree of intellectual disability, the ability to provide consent will depend on the cognitive ability of the individual.

A copy of the completed consent form will be made available to all participants.

VII. Data Analysis and Reporting

The following analyses are planned

1. Trends in weight and BMI change over 6 months.
2. Description of factors that could affect weight and BMI in this group, including food access, change in living situation, physical activity and medication.

VIII. Facilities and Performance Sites

This study will use mobile health technology. Interested participants will sign an informed consent and provide a mobile phone number on which they are able to send and receive text messages. FPWR will assign each participant a unique, random, study-related ID, not linked to any identifying information (eg. fpwr2018_001). Only this unique ID will be used on the Mosio platform. The key to the IDs will only be available to researchers associated with this study. Once registered, participants will receive text messages and surveys at pre-determined intervals on their mobile phones (discussed above) and will respond directly via text. Mosio will store all data on a secure server and provide investigators a login to the site. Only study personnel will be able to access the data.

IX. Potential Benefits

There is no direct benefit to the patient from participating in the study. As mentioned above, real-world studies are essential in PWS to understand the natural progression of the disease. At the end of the study, participants will receive a personalized chart detailing their weight progression over the course of the study.

X. Potential Risks, Discomforts, Inconveniences, and Precautions

Participation in the study presents minimal risks to its participants. The greatest risk is loss of confidentiality of personal health information.

XI. Risk/Benefit Analysis:

This is a minimal risk study without direct benefits to the individual. There are no risks of physical harm associated with participation in the study. While every effort will be made to keep data confidential there is a potential risk of a breach of confidentiality of medical information and associated privacy of the participants. This risk will be minimized by storing data on a secure server. Only authorized study personnel will have access to the data.

XII. Privacy and Confidentiality:

Participants' privacy and confidentiality will be safeguarded by using modern database management techniques and informed consent. Only authorized study personnel will have access to the data.

Data will be stored for up to one year after completion of the study. Deidentified data will be stored indefinitely.

Only de-identified information will be used for potential publications or sharing with the community.

XIII. Cost of Participation

There is no cost to participating in the study. Participants will be informed that they are responsible for any charges related to sending/receiving text messages on their mobile phones.

XIV. Payment for Participation

There will be no reimbursements made to participants.

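### Diet is a named factor in objective 2 and the Background promises to survey it, but no data item asks about diet and section VII does not list it

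*Protocol*

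**What the plan says.** Section I, objective 2, sets out to "Study factors that could directly or indirectly affect weight change such as diet, medication, food access and environment". Section II gives the reasoning: "Weight may also be influenced by living situation, diet, medication and access to food". The next sentence draws the consequence for data collection: "Therefore, we will also survey participants on diet and medication changes and food access", and adds that the part these play in any weight change will be studied.

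Section III lists the data to be collected. The survey at months 3 and 6 includes a food-access question, "To your knowledge has access to food at home or outside the home increased/decreased/stayed the same for the person with PWS", and a medication question, "Has there been medication change in the last 3 months for the person with PWS". Its other items are living situation, activity level and height. The baseline survey and the weekly text contain nothing on diet.

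Section VII, item 2, plans a "Description of factors that could affect weight and BMI in this group, including food access, change in living situation, physical activity and medication".

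**The concern.** The objective and the Background say that diet will be studied and surveyed. The sections that say what will be asked and what will be analysed do not mention it. The protocol writes out its questions one by one, so this is a mismatch within the document and not a detail left for later.

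What is at stake is one named component of a primary objective. A statistical analysis plan can choose models and handle missing values, but it cannot analyse a variable that nobody was asked about. Six months of diet changes cannot be reliably rebuilt afterwards. The study could not even tabulate whether participants whose food access changed also changed their diet, although the protocol treats these as two separate influences on weight.

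**Working it through.** No sample-size or power figure is involved. The check is a count of the listed items and a comparison of sections.

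**Step 1. Count the items in section III.**

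| Time | Items | Number | On diet |
|---|---|---|---|
| Baseline | Diagnosis by blood test; gender; age; growth hormone therapy; past weighing frequency | 5 | 0 |
| Weekly | Weight | 1 | 0 |
| Months 3 and 6 | Living situation; food access; activity level; medication change; height | 5 | 0 |
| Total | | 5 + 1 + 5 = 11 | 0 |

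Follow-up items 1 to 5 are numbered without a gap, so nothing suggests that a diet question was lost in the text.

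**Step 2. Trace each factor through the protocol.**

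| Factor | Objective 2 | Background: influences on weight | Background: to be surveyed | Section III item | Section VII, item 2 |
|---|---|---|---|---|---|
| Diet | Named | Named | Named | None | Not named |
| Medication | Named | Named | Named | Follow-up item 4 | Named |
| Food access | Named | Named | Named | Follow-up item 2 | Named |
| Environment or living situation | Named (environment) | Named (living situation) | Not named | Follow-up item 1 | Named |
| Activity | Not named | Not named | Not named | Follow-up item 3 | Named |

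Of the four factors in objective 2, 3 have an item. This takes living situation as the measure of environment, which it covers at least in part. Of the three topics in the Background's survey commitment, 2 have an item. Diet is the missing one in both counts.

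Activity shows the reverse pattern: neither the objective nor the Background sentences name it, yet it is asked about and analysed. The four factors in section VII, item 2, are those of follow-up items 1 to 4. The analysis section therefore agrees with the questionnaire, and the break lies between those two sections and the stated aims. That looks like an oversight and not a decision to drop diet.

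**Step 3. Ask whether another item covers diet.** The nearest is food access. It records only whether access went up, went down or stayed the same, and says nothing about what is eaten or whether the diet changed. Either can change without the other. The protocol itself lists the two separately in objective 2 and in both Background sentences.

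**Step 4. Size.** At the target of 300 participants with 2 follow-up surveys each, 300 × 2 = 600 surveys at most would be sent, with 0 diet questions among them. The 600 assumes full recruitment; the finding itself is the count of 0 in 11.

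**The case against.** The best reply is that the lists are open. Objective 2 introduces its factors as examples, and section VII, item 2, gives its list as inclusive and not exhaustive, so neither strictly contradicts the other. This is right as far as it goes, and it narrows the firm conflict to the Background commitment against the item list in section III. It does not remove that conflict. The Background sentence is an unqualified statement that diet changes will be surveyed, and an open analysis list is of no help if there are no diet data to add.

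A second reply is that food access is a partial proxy, and that the living-situation question, whose examples are open-ended, might pick up some relevant changes. Some incidental information may arrive this way. It would be unsystematic, and the protocol's own distinction between diet and food access means that one does not stand in for the other.

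A third reply is that the message sequences could carry further questions when they are set up. The protocol lists what is to be collected, and diet is not there; reliance on questions not shown would be speculation.

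One caution stands. In an uncontrolled, descriptive study, a reported yes/no diet item would not isolate the effect of diet from that of food access. What it would give is a record of diet change that can be described beside the other factors, and this is all that section VII, item 2, sets out to do.

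**Conclusion.** The point holds. None of the 11 listed items covers diet, and diet is the only one of the four factors named in objective 2 without a question. The diet part of that objective cannot be addressed from the data as planned. The conclusion rests on reading the list in section III as the full set of questions and on taking diet and food access as distinct, as the protocol does.

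The effect is limited. Objectives 1 and 3, and the description of medication, food access, living situation and activity, are untouched. It should be fixed, because part of a primary objective is lost and the remedy is cheap, but it does not threaten the study as a whole.

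**What to change.** Either of two changes reconciles the sections.

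- **Collect diet.** Add one item to the survey at months 3 and 6 that asks whether the participant's diet has changed over the preceding three months, yes or no, with a short free-text follow-up on what changed. Add diet to the factor list in section VII, item 2. The exact wording is for the sponsor. A baseline diet item is optional, since the Background commitment concerns changes.
- **Do not collect diet.** Remove it from objective 2 and from the survey commitment in the Background.

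The first option takes the follow-up survey from 5 to 6 items, which is 1 item × 2 time points = 2 extra questions per participant over the study, plus a small edit to section VII. The second costs a wording change only, but gives up a factor that the protocol itself says may influence weight. The first is preferable if the questionnaire can still be changed.

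### Height is first asked for at month 3, so the 6-month height change and 6-month BMI change have no measured baseline

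*Protocol*

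**What the plan says.** - **Section I, Objectives, item 3** (under the primary objectives): "Collect data on participant height change over 6 months to calculate body mass index (BMI".
- **Section VII, Data Analysis and Reporting, item 1:** "Trends in weight and BMI change over 6 months".
- **Section III, Data to be collected, item 1:** the "Initial Survey at baseline only" covers blood-test diagnosis, gender, age, growth hormone history and how often the person was weighed in the past 6 months. Height is not on the list.
- **Section III, item 2:** weight is reported "Once a week, every week, for 6 months". The text message asks for weight only.
- **Section III, item 3:** "At 3 months and 6 months participants will answer a survey". Item 5 of that survey is "Please record participant's height". This is the only place where the protocol asks for height.
- **Section V.a:** the population is "Male and female individuals diagnosed with PWS, 12 years and older". Growth hormone use is recorded at baseline and is not an exclusion.

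**The concern.** The objective and the planned analysis call for change over 6 months, but the data collection gives a first height halfway through that period. Objective 1 uses the same 6-month span for weight, and weight is collected across all of it. The natural reading is that height and BMI should cover it too.

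At stake is whether a primary objective can be met. BMI needs a weight and a height from about the same time. Weekly weights begin at the start, but for the first 3 months there is no height to pair with them. For a participant who is still growing, the analyst must impute the baseline height or report a shorter interval than the one stated. The simplest imputation, carrying month-3 height back, produces an error that always points the same way: BMI gain looks too large. A larger sample does not remove it. Because it depends on growth, it also distorts comparisons between adolescents and adults, and Section II names data across age groups as a need.

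**Working it through.** **Step 1. Interval stated against interval observed.**

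- Stated (Section I item 3; Section VII item 1): 6 months.
- Scheduled heights (Section III item 3): months 3 and 6.
- Observable interval = 6 − 3 = 3 months.

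The stated interval cannot be reproduced from the schedule. The protocol names no other source of baseline height; the Global PWS Registry appears in Section V.d only as a recruitment channel.

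**Step 2. Error in baseline BMI if month-3 height is carried back.** The protocol gives no heights, weights or growth rates, so the inputs are assumptions: baseline height h0 = 150 cm, true baseline BMI 30 (weight w = 30 × 1.50² = 67.5 kg), and linear growth of v cm/year, so that month-3 height h3 = h0 + v/4.

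Error = w/h3² − w/h0², heights in metres.

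| v (cm/year) | h3 (cm) | Error in baseline BMI (kg/m²) |
|---|---|---|
| 2 | 150.5 | −0.20 |
| 4 | 151.0 | −0.40 |
| 6 | 151.5 | −0.59 |
| 8 | 152.0 | −0.78 |

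Month-6 BMI is measured correctly, so the BMI change is overstated by the same amounts.

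**Step 3. A single participant.** Assumed: weight 60 to 63 kg, growth 6 cm/year, heights 150, 151.5 and 153 cm at months 0, 3 and 6.

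- True baseline BMI: 60/1.50² = 26.67
- Baseline BMI with month-3 height: 60/1.515² = 26.14
- Month-6 BMI: 63/1.53² = 26.91
- True change: 26.91 − 26.67 = +0.25 (0.246 unrounded)
- Change with month-3 height: 26.91 − 26.14 = +0.77

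The absolute overstatement is about 0.5 kg/m².

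**Step 4. Sensitivity to the assumptions.** Weight 60 kg at baseline and 62 kg at month 6, linear growth, baseline height 145 or 155 cm:

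| v (cm/year) | 145 cm: true / with month-3 height / bias | 155 cm: true / with month-3 height / bias |
|---|---|---|
| 0 | 0.95 / 0.95 / 0.00 | 0.83 / 0.83 / 0.00 |
| 2 | 0.55 / 0.74 / 0.20 | 0.50 / 0.66 / 0.16 |
| 4 | 0.15 / 0.54 / 0.39 | 0.18 / 0.50 / 0.32 |
| 6 | −0.23 / 0.35 / 0.58 | −0.14 / 0.34 / 0.48 |
| 8 | −0.61 / 0.16 / 0.77 | −0.45 / 0.18 / 0.63 |

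At 6 and 8 cm/year the sign reverses: BMI falls but appears to rise. With no growth there is no bias.

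**The case against.** The gap in the schedule is not in dispute. The case on the other side concerns how much it matters.

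- **Baseline height can be estimated.** Under linear growth, h0 = 2·h3 − h6. In the Step 3 example this gives 2 × 151.5 − 153 = 150 cm, with no bias, so carrying month-3 height back is not the only choice. This stands, but the method is weak. It needs both heights and assumes linear growth. With independent measurement errors of standard deviation σ, the estimate has standard deviation √(4 + 1)·σ = √5·σ, about 2.2σ. The 6-month height change becomes 2·(h6 − h3), which is the 3-month change doubled. It is an imputation, not a measurement.
- **Adults of stable height are little affected.** This stands. For them month-3 height serves well, and the BMI problem is mainly one for participants who are still growing. The protocol does not state or plan for that substitution.
- **The size across the cohort is unknown.** This stands. The protocol gives no age mix, growth rate or share on growth hormone.
- **A ratio would depend on the example.** In Step 3 the change is about three times too large, mainly because the true change is small. With the same growth and a gain from 60 to 66 kg, the true change is 1.53 against 2.05, a ratio of 1.34. The absolute error is the safer summary.
- **Early leavers.** Someone who leaves before month 3 has no 6-month BMI change under any schedule. What the present schedule takes from them is a baseline BMI and any early BMI values.
- **Weight is untouched.** Objective 1 is unaffected, and BMI at months 3 and 6 can still be calculated.

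These points limit the reach of the problem. None supplies a baseline height.

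**Conclusion.** The concern holds. As written, the protocol measures height change over 3 months, not 6, and the planned 6-month BMI change has no measured baseline. That follows from the schedule alone and needs no assumption. Choices made in a statistical analysis plan cannot repair it, because the value is never collected.

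The size of the resulting error does rest on assumptions. With month-3 height carried back and linear growth of 2 to 8 cm/year, BMI gain is overstated by 0.20 to 0.78 kg/m² at 150 cm and baseline BMI 30, and by 0.16 to 0.77 kg/m² over the Step 4 range. It is near zero for adults of stable height, and its average over the cohort cannot be worked out from the protocol. The change should be made: a stated primary objective is affected, and a baseline height not asked for on time cannot be measured later.

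**What to change.** Add the existing height question to the baseline survey in Section III item 1, answered at the time of the first weekly weight, and keep the heights at months 3 and 6. State in Section VII that 6-month height and BMI change are calculated from baseline to month 6. Heights then fall at months 0, 3 and 6, the interval is 6 − 0 = 6 months, and a missed month-3 survey no longer removes the height change.

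The cost is one more text question and a short wording change, with no extra visits or staff. It has to be in place before participants pass baseline.

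If baseline height cannot be added, restate objective 3 and planned analysis 1 so that height and BMI change run from month 3 to month 6. That makes the protocol consistent but gives up half of the intended period for height and BMI.

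### No survey asks for weight, so a participant who has stopped the weekly texts but answers the 6-month survey has no month-6 weight or BMI to set beside those answers

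*Protocol*

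**What the plan says.** All references are to the Protocol.

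- **Objectives (I).** Objective 1 concerns weight change over 6 months in people with PWS aged 12 and over. Objective 2 concerns factors that may affect it. Objective 3 collects height for BMI.
- **Weight (III, item 2).** Collected "Once a week, every week, for 6 months", by this route: "Participants will be sent a pre-scheduled text message reminder to weigh in and send a text response with the" participant's weight.
- **Initial Survey (III, item 1).** Covers diagnosis, gender, age, growth hormone history and past weighing habits ("In the past 6 months, approximately how often did you weigh your child with PWS"). It records no weight and no height.
- **3- and 6-month surveys (III, item 3).** Five questions. The first is "Has there been any change in the living situation for the person with PWS in the last 3 months", with the examples "moved, change in primary caregiver, illness in the family". The next three cover food access, activity and medication. The fifth is "Please record participant's height". None asks for weight.
- **Contact route (VIII).** Participants "provide a mobile phone number on which they are able to send and receive text messages". Weekly texts and surveys both arrive on that phone.
- **Analysis (VII).** Trends in weight and BMI over 6 months, and a description of the factors that could affect them.

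**The concern.** Weight is the outcome of objective 1 and the numerator of BMI, yet each weight depends on a reply to one weekly prompt. The surveys collect the other half of BMI (height) and the factor data without asking for weight at the same time.

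A participant who tires of weekly weighing may still answer two short surveys. That person's 6-month height then has no weight beside it, and the factor answers, which look back 3 months, describe a period with few or no weights.

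The late trend, and its relation to the factors, would then rest on families who kept weighing. If stopping is related to weight or to a change in living situation, that part of the analysis can be biased. No analysis plan can repair this later, because it cannot use a weight that was never requested.

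**Working it through.** The protocol gives no figure to reproduce on this point. The target of 300 carries no reply or dropout rate. The main check is a reading of the item lists, followed by three illustrations under stated assumptions.

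**1. What is asked, and when**

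| Time | Survey: weight | Survey: height | Survey: factors over last 3 months | Weekly text: weight |
|---|---|---|---|---|
| Baseline | no | no | no | first weekly reply, if sent |
| Month 3 | no | yes | yes | yes, if still replying |
| Month 6 | no | yes | yes | yes, if still replying |

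Weight depends on the weekly reply in every row. For someone who has stopped replying, the month-6 row holds height and factors only.

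**2. Does occasional non-reply matter?**
Six months is 365.25 / 2 / 7 = 26.1 weeks, so about 26 weights are scheduled. Assume independent weekly replies with probability p. The chance of at least one weight in the last 4 weeks is 1 − (1 − p)^4:
- p = 0.3: 1 − 0.7^4 = 0.76
- p = 0.5: 1 − 0.5^4 = 0.94
- p = 0.7: 1 − 0.3^4 = 0.99
- p = 0.9: 1 − 0.1^4 = 0.9999

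Occasional misses seldom remove the late weight. The problem is lasting lapse, which independent replies do not describe.

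**3. What does a lapsed family still contribute to a trend?**
For m equally spaced weekly readings, the sum of squares of time about its mean is S(m) = m(m² − 1)/12. With independent errors, the standard error of a within-person slope relative to a full series is √[S(26)/S(m)].
- S(26) = 26 × 675 / 12 = 1462.5
- Stops after 20 readings: S(20) = 20 × 399 / 12 = 665; ratio √(1462.5/665) = 1.5
- Stops after 13 readings: S(13) = 13 × 168 / 12 = 182; ratio √(1462.5/182) = 2.8

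The earlier readings keep some information about the slope. A family that stops at about week 13, however, has no weight in the 3 months that the 6-month survey asks about. One that stops at week 20 has weights for only about half of them.

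**4. How many month-6 weights could a survey item recover?**
Recovered = 300 × (share lapsed) × (share of those who answer the 6-month survey). Both shares are assumptions.

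| Lapsed | Number | 25% answer | 50% answer | 75% answer |
|---|---|---|---|---|
| 10% | 30 | 7.5 | 15 | 22.5 |
| 20% | 60 | 15 | 30 | 45 |
| 40% | 120 | 30 | 60 | 90 |

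The range is about 8 to 90 of 300. It is this wide because the protocol gives neither share.

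**The case against.** The strongest objection is that the gap is narrow. The planned analysis is of trends, and no two-point change from baseline to month 6 is named. A lapsed family keeps its earlier weights, weekly prompts are scheduled around months 3 and 6 anyway, and occasional misses rarely remove the late value. The group affected is those who ignore weight texts yet answer a survey on the same phone. All of this stands, and it limits the point to the month-6 value and the later part of the trend. A reader might infer that such families lose the endpoint altogether; the analysis section does not support that.

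A reader might also infer that a move or a change of caregiver cuts off the weights while the survey still gets through. VIII does not support this. Surveys go to the same phone as the weekly texts, so if that phone is lost to the family, the survey is lost too and a weight item in it recovers nothing. The protocol is also silent on updating a number; it does not forbid it.

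Third, the Initial Survey has no height item, so adding weight there gives a starting weight but no baseline BMI. That is correct. The addition serves only those who never send a weekly weight.

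Finally, missing-data handling commonly belongs in the analysis plan, which is not shown. That does not answer the point, which concerns what is collected. Lapse is foreseeable from the protocol itself: its baseline question allows for families who weigh less than monthly or only at doctor visits, weekly weighing is then asked of them for 6 months, there is no payment (XIV), and they bear any text charges (XIII).

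**Conclusion.** The gap is real but modest. No survey contains a weight item. A participant who has stopped the weekly replies but answers the 6-month survey therefore has no month-6 weight or BMI, and has no weights for whatever part of the preceding 3 months follows the lapse (all of it, if the lapse came by month 3). Earlier weights still inform the trend.

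The later trend and its relation to the factors can be biased if lapse is related to weight or living situation. The protocol does not show that it is. Nor does it give a reply rate, so the size is unknown, and a bias in kilograms cannot be supported from it. The 8 to 90 recovered weights rest wholly on the assumed 10-40% lapse and 25-75% survey response.

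The change is worth making because it costs almost nothing and cannot be made after data collection.

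**What to change.** Add an item for current weight and the date weighed to the 3- and 6-month surveys, beside height. Add the same item to the Initial Survey, so that those who never send a weekly weight have a starting weight.

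Use the survey weight as a back-up only where no weekly weight exists near that date, and state that the weekly reply takes priority when both are present.

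The cost is one more item in each of three automated surveys and some duplication of same-week texts, which the priority rule settles. The change does not help when the registered phone no longer reaches the caregiver.
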